7.2. Participant Discontinuation/Withdrawal from the Study

Participants will be discontinued in the following circumstances:

- enrollment in any other clinical study involving an investigational product or enrollment in any other type of medical research judged not to be scientifically or medically compatible with this study
- participation in the study needs to be stopped for medical, safety, regulatory, or other reasons consistent with applicable laws, regulations, and good clinical practice (GCP)
- patient decision
 - the patient or the patient's designee requests to be withdrawn from the study
- the patient becomes pregnant during the study. See Section 8.3 regarding regulatory reporting requirements on fetal outcome.

Participants discontinuing from the study prematurely for any reason should complete AE and other safety follow-up per Section 1.3 (Schedule of Activities), Section 8.3 (Adverse Events and Serious Adverse Events), and Section 8.2 (Safety Assessments).

Participants who withdraw their consent from the study and request to discard their genetic and biomarker samples will have their samples destroyed. Analysis results that are available before the consent withdrawal may be published in articles or other disclosures without an identifiable individual patient information.

7.2.1. Discontinuation of Inadvertently Enrolled Participants

If the sponsor or investigator identifies a participant who did not meet enrollment criteria and was inadvertently enrolled, then the patient should be discontinued from study treatment unless there are extenuating circumstances that make it medically necessary for the patient to continue on study treatment. If the investigator and the sponsor CRP/CRS agree it is medically appropriate to continue, the investigator must obtain documented approval from the sponsor CRP/CRS to allow the inadvertently enrolled participant to continue in the study with or without

treatment with investigational product. Safety follow up is as outlined in Section 1.3 (Schedule of Activities), Section 8.3 (Adverse Events and Serious Adverse Events), and Section 8.2 (Safety Assessments) of the protocol.

7.3. Lost to Follow-Up

A participant will be considered lost to follow-up if he or she repeatedly fails to return for scheduled visits and is unable to be contacted by the study site. Site personnel are expected to make diligent attempts to contact participants who fail to return for a scheduled visit or were otherwise unable to be followed up by the site.

Site personnel, or an independent third party, will attempt to collect the vital status of the participant within legal and ethical boundaries for all participants randomized, including those who did not get investigational product. Public sources may be searched for vital status information. If vital status is determined, this will be documented and the participant will not be considered lost to follow-up.

Lilly personnel will not be involved in any attempts to collect vital status information.

Discontinuation of specific sites or of the study as a whole are handled as part of Section 10.1.7.2.

8. Study Assessments and Procedures

- Unless otherwise stated in the subsections below, all samples collected for specified laboratory tests will be destroyed within 60 days of receipt of confirmed test results. Certain samples may be retained for a longer period, if necessary, to comply with applicable laws, regulations, or laboratory certification standards.
- Study procedures and their timing are summarized in the SoA (Section 1.3). Protocol waivers or exemptions are not allowed.
- Immediate safety concerns should be discussed with the sponsor immediately upon occurrence or awareness to determine if the participant should continue or discontinue study intervention.
- Adherence to the study design requirements, including those specified in the SoA (Section 1.3), is essential and required for study conduct.
- All screening evaluations must be completed and reviewed to confirm that potential participants meet all eligibility criteria. The investigator will maintain a screening log to record details of all participants screened and to confirm eligibility or record reasons for screening failure, as applicable.
- Procedures conducted as part of the participant's routine clinical management (eg, blood count) and obtained before signing of the ICF may be utilized for screening or baseline purposes provided the procedures met the protocol-specified criteria and were performed within the time frame defined in the SoA (Section 1.3).
- Repeat or unscheduled samples may be taken for safety reasons or for technical issues with the samples.

8.1. Efficacy Assessments

Tumor assessments will be performed for each patient at the times shown in the SoA (Section 1.3).

Response Evaluation Criteria in Solid Tumors v1.1 (Eisenhauer et al. 2009) and iRECIST (Seymour et al. 2017) will be applied as the primary criteria for assessment of tumor response and date of tumor progression. The method of tumor assessment used at baseline must be used consistently throughout the study. Local tumor imaging (investigator assessment with site radiological reading) will be used. See Section 8.1.1 for detailed information regarding iRECIST for immune-based therapies.

Computed tomography (CT) scans, including spiral CT, are the preferred methods of measurement (CT scan thickness recommended to be ≤ 5 mm); however, magnetic resonance imaging is also acceptable in certain situations, such as when body scans are indicated or if there is a concern about radiation exposure associated with CT. Intravenous and oral contrast are required unless medically contraindicated.

See Section 9.4.3 for definitions of the efficacy endpoints.

8.1.1. iRECIST for Immune-Based Therapies

Rationale of Using iRECIST after First Radiologic PD by RECIST 1.1

The response to immunotherapy may differ from the typical responses observed with cytotoxic chemotherapy, including the following (Wolchock et al. 2009; Nishino et al. 2013):

- Response to immunotherapy may be delayed.
- Response to immunotherapy may occur after progressive disease by conventional criteria.
- The appearance of new lesions may not represent progressive disease with immunotherapy.

Therefore, to adequately characterize additional patterns of response and progression specific to patients treated with immunotherapy, which cannot be captured using conventional criteria such as RECIST v1.1, alternative measures of tumor assessment have been developed. The iRECIST standard was developed by the RECIST working group for the use of modified RECIST version 1.1 in cancer immunotherapy trials (Seymour et al. 2017).

After initial disease progression defined by RECIST 1.1, iRECIST guidelines will be applied in the following tumor assessments. In iRECIST, any new lesions are categorized as measurable or non-measurable. Up to 5 lesions total (up to 2 per organ) can be selected as new lesion-target (NL-T). All other new lesions will be followed as new lesion-non-target (NL-NT). The NL-T sum of diameters will be calculated and recorded separately from the sum of diameters for target lesions identified at baseline.

Tumor response by iRECIST will be classified as confirmed progression (iCPD), or unconfirmed progression (iUPD), or stable disease or response (iSD/iPR/iCR) at all subsequent imaging. The initial tumor scan showing disease progression by RECIST 1.1 will be assigned as unconfirmed progression (iUPD) for overall response.

Progression is considered confirmed (iCPD), if the previous response status was iUPD and any of the following happens:

- For target lesions: any further increase in the previously identified target lesion sum of diameters by 5mm or more after iUPD.
- For non-target lesions: any further increase in the size of previously identified non-target lesion iUPD (the increase doesn't need to meet RECIST 1.1 criteria for unequivocal progression)
- For new lesions:
 - an increase in the NL-T previously identified as iUPD and increase ≥ 5 mm in sum of diameter OR
 - any increase for NL-NT OR
 - any appearance of additional new lesions

The overall response remains iUPD, IF

- target lesions were the cause of the initial iUPD AND
- target lesions haven't worsened, but they are still above PD threshold (20% increase from the nadir), AND
- no above factors of iCPD occur.

When progression is considered not unconfirmed, the overall response can become iSD/iPR/iCR instead of iUPD if any of the following criteria are met:

- iCR: Target lesions and non-target lesions have regressed completely AND no new lesions.
- iPR: Target lesions have regressed to $\geq 30\%$ decrease from baseline (iCR or iPR) AND non-target lesions remain non-iCR/non-iUPD AND no new lesion
- iSD: Target lesions have regressed to $< 20\%$ increase from nadir AND non-target lesions remain non-iCR/non-iUPD AND no new lesion.

Imaging and Treatment Guideline for Patients Who Have Radiologic Evidence of Progressive Disease by RECIST 1.1

If a patient is clinically stable at the first radiologic PD by RECIST 1.1, the patient should not be discontinued from the study until progression is confirmed no less than 4 weeks and no more than 8 weeks later by iRECIST. The continuation of treatment after initial radiologic PD takes into consideration the observation that some patients may experience transient tumor flare or pseudoprogression with immunotherapy, but could have disease response later. Patients who receive confirmatory imaging do not need to undergo the next scheduled tumor imaging if it is less than 4 weeks later; tumor assessment will resume at the next scheduled imaging time point, if clinically stable. Patients will be discontinued from study treatment if disease progression is confirmed by iRECIST (Seymour et al. 2017).

If a patient is clinically unstable, the patient should be discontinued from the study treatment at the first radiological PD by RECIST 1.1. The repeat tumor imaging for confirmation of PD by iRECIST is not required.

Clinical stability is defined as the following (Seymour et al. 2017): no worsening of performance status; absence of signs or symptoms that are associated with clinically significant disease progression; no requirement for intensified management, including increased analgesia, radiotherapy, or other palliative care. Clinical stability is ultimately defined by the treating investigator.

A summary of imaging and treatment guidelines for patients who have first radiologic PD is listed in the table below.

Imaging and Treatment Guideline for Patients who have First Radiologic PD by RECIST 1.1

	Clinically Stable		Clinically Unstable	
	Imaging	Treatment	Imaging	Treatment
First radiologic evidence of progressive disease by RECIST 1.1	Repeat imaging at 4 to 8 weeks to confirm PD by iRECIST	May continue study treatment while waiting for confirmatory scan by iRECIST	Not required; Repeat imaging at 4 to 8 weeks to confirm PD per investigator's discretion only	Discontinue treatment
Repeat tumor imaging confirms PD (iCPD) by iRECIST	No additional imaging required	Discontinue treatment	No additional imaging required	Not applicable
Repeat tumor imaging shows iUPD by iRECIST	Repeat imaging at 4 to 8 weeks to confirm PD by iRECIST. May occur at next regularly scheduled imaging visit	Continue treatment at the investigator's discretion	Repeat imaging at 4 to 8 weeks to confirm PD per investigator's discretion only	Discontinue treatment.
Repeat tumor imaging shows iSD, iPR, or iCR by iRECIST per Investigator assessment.	Continue regularly scheduled imaging assessments.	Continue study treatment at the Investigator's discretion.	Continue regularly scheduled imaging assessments.	Discontinue treatment

Abbreviations: iCPD = iRECIST confirmed progressive disease; iCR = iRECIST confirmed complete response; iSD = iRECIST confirmed stable disease; iUPD = iRECIST unconfirmed progressive disease; RECIST = Response Evaluation Criteria in Solid Tumors.

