5.4.8.3. Exploratory Efficacy Analyses

Overall survival, as well as the efficacy parameters based on iRECIST, will also be analyzed as the exploratory objectives.

The efficacy parameters based on iRECIST will also be analyzed as the exploratory objective.

Overall response rate (iORR) is measured by the percentage of patients who achieved a iCR or iPR as their best overall response (iBOR) out of all treated patients (safety population). The

iBOR is defined as the best response across all time point assessments based on RECIST 1.1 and iRECIST.

Progression-free survival (iPFS) should be the date of randomization (the date of first dose for single-arm study) to the date at which progression criteria are first met (that is, the date of first unconfirmed progression [iUPD]) provided that iUPD or a sequence of consecutive iUPDs is confirmed by a confirmed progression (iCPD), the iUPD followed by only iUPDs at subsequent assessments, no more tumor assessments, or to the death date from any cause in the absence of progressive disease. Patients known to be alive and without the iUPD as mentioned above as of the data inclusion cut-off date for a particular analysis will be censored at the time of the last adequate tumor assessment (a detailed iPFS event/censoring scheme is provided in the table below).

Table JZIA.5.3. Progression-Free Survival (iPFS) Event/Censoring Scheme

Situation ^a	Event/Censor	Date of Event or Censor
iUPD confirmed at next assessment (iCPD) or consecutive iUPD followed by an iCPD	Event	(First) iUPD date
iUPD followed by only iUPD at subsequent assessments and no further tumor assessment available.	Event	First iUPD date of the consecutive iUPDs
iUPD without subsequent assessment	Event	iUPD date
Death	Event	Death date if no iUPD date as in the above 3 situations before death.
No Death and no iUPD or iUPD is followed by iSD/iPR/iCR/	Censored	Date of last adequate tumor assessment per iRECIST, or date of randomization (first dose for single-arm study) (whichever is later) ^b
Confirmed iUPD (iCPD) or death reported after 2 scan intervals following the last adequate tumor scan	Censored	Date of last adequate tumor scan prior to confirmed iUPD (iCPD) or death
No baseline radiologic tumor assessment available	Censored	Date of randomization (first dose for single-arm study)

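### Protocol Section 8.1.1 denies iPR and iSD to a patient whose non-target lesions have cleared, and states a rule for remaining iUPD only where target lesions caused it

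*Protocol*

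**What the plan says.** Protocol Section 8.1.1 labels the first RECIST 1.1 progression as iUPD, whatever its cause, and says that tumor response "will be classified as confirmed progression (iCPD), or unconfirmed progression (iUPD), or stable disease or response (iSD/iPR/iCR) at all subsequent imaging". It then gives the rules:

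- **iCPD.** The target-lesion criterion reads "any further increase in the previously identified target lesion sum of diameters by 5mm or more after iUPD". Progression is also confirmed if non-target disease grows at all, or if new lesions grow or more of them appear.
- **Remains iUPD.** Three conditions joined by AND. The first reads "target lesions were the cause of the initial iUPD AND"; the second reads "target lesions haven't worsened, but they are still above PD threshold (20% increase from the nadir), AND"; the third is that no iCPD criterion is met.
- **iCR.** Target and non-target lesions completely regressed, no new lesions.
- **iPR and iSD.** A target-lesion condition (at least 30% below baseline, or less than 20% above nadir), and in both cases "AND non-target lesions remain non-iCR/non-iUPD AND no new lesion".

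The lead-in to the last two items says the response can become one of these instead of iUPD. It speaks of progression being not unconfirmed, evidently a slip for not confirmed.

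SAP Section 5.4.8.3 uses the labels without defining how they are assigned. In Table JZIA.5.3, "iUPD followed by only iUPD at subsequent assessments and no further tumor assessment available" is an iPFS event dated at the first of the consecutive iUPDs, and an iUPD with no subsequent assessment is also an event. An iUPD followed by iSD, iPR or iCR is censored at the last adequate assessment. Footnote b counts an assessment as adequate only if it carries one of the five iRECIST labels.

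**The concern.** The rules should place every follow-up scan in one category, because the category fixes the endpoint. As written, complete clearance of non-target lesions counts against the patient: the same target shrinkage earns iPR if non-target disease persists and no response label if it has gone. Response after conventional progression is one of the patterns for which Section 8.1.1 adopts iRECIST, so the fault lies where the criteria are meant to help.

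The rule for remaining iUPD mentions only target lesions, although iUPD may equally arise from non-target progression or a new lesion. Tumor assessment is local (Protocol Section 8.1), so each site would have to supply the missing rule, and iORR, iPFS and iDoR could rest on differing conventions.

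**Working it through.** No sample-size or error-rate figure is involved. The check applies the stated rules to every possible follow-up scan.

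**1. The cleared non-target case.** Take iUPD of any cause, then a scan with target lesions down 40%, all non-target lesions gone and no new lesion.

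- iCPD: no, nothing has grown.
- Remains iUPD: no, target lesions are not above the PD threshold.
- iCR: no, target lesions remain.
- iPR: no, non-target lesions are iCR, not non-iCR/non-iUPD.
- iSD: no, same non-target condition.

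The same failure occurs with target lesions at SD.

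**2. All states.** Five target states × four non-target states × three new-lesion states = 60. Growth in any category gives iCPD. The rest number 4 × 3 × 2 = 24, so 60 − 24 = 36 are iCPD. The table shows the label for each of the 24, allowing target lesions to be among the causes of iUPD and reading no new lesion as none present (NT = non-target).

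| Target lesions | NT cleared, no new lesion | NT non-iCR/non-iUPD, no new lesion | NT iUPD unchanged, no new lesion | New lesion unchanged (3 NT states) |
|---|---|---|---|---|
| Cleared | iCR | iPR | none | none × 3 |
| At least 30% below baseline | **none** | iPR | none | none × 3 |
| Less than 20% above nadir | **none** | iSD | none | none × 3 |
| Above PD threshold, not worse | iUPD | iUPD | iUPD | iUPD × 3 |

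Labelled: 6 iUPD + 2 iPR + 1 iSD + 1 iCR = 10. Unlabelled: 24 − 10 = 14, made up of 9 with an unchanged new lesion, 3 with unchanged non-target iUPD and no new lesion, and the 2 in bold.

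**3. Sensitivity to the reading.**

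- If iUPD is the implied default, the 9 + 3 = 12 stay iUPD, which is sensible. The 2 in bold would also stay iUPD, although no lesion still shows progression.
- If no new lesion means no *additional* one, 4 of the 9 new-lesion states gain a label (1 iCR, 2 iPR, 1 iSD), leaving 14 − 4 = 10 unlabelled. The 2 in bold and the 3 non-target states are unaffected. This reading would also allow iCR with a new lesion still present.

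**4. Finer grid.** Separating the causes of iUPD (target, non-target, new lesion and their mixtures) gives 308 combinations, of which 99 are not iCPD. Of those, 56 are unlabelled on the first reading of no new lesion and 40 on the second. The bold pair appears under each of the 7 cause sets: 2 × 7 = 14 of the 99. These are rule combinations, not patients.

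**5. Effect on endpoints for the bold pair.**

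- *Default iUPD:* if later scans look the same and assessment then stops, Table JZIA.5.3 gives an event at the first iUPD. Labelled iPR or iSD, the patient is censored. If target lesions later clear too, the scan becomes iCR and the patient is again censored.
- *Unlabelled:* the scan is not adequate under footnote b. If it therefore does not count as a subsequent assessment, the row for iUPD without one applies, again an event.
- *iORR and iDoR:* only the PR variant matters, and only if the patient has no other qualifying response. Taking planned cohort sizes as denominators, one such patient moves iORR by 1/40 = 2.5 points (D1 or D2), 1/30 = 3.3 points (D3) or 1/8 = 12.5 points (C1 or C2).

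**The case against.** The text says the response remains iUPD if, not only if, the listed conditions hold, and speaks of becoming iSD, iPR or iCR instead of iUPD. That suggests iUPD persists until iCPD or a listed exit. This stands, and it disposes of 12 of the 14 unlabelled states. For those 12 the iPFS result may not change anyway: continued iUPD and iUPD without a further assessment are both events at the iUPD date. The default does not help the cleared non-target case.

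Section 8.1.1 also says that iRECIST guidelines apply and cites the published standard, so a site might fill the gap from there. That is fair, but nothing says the cited standard overrides the protocol's own rules.

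A reader might go further on three counts, none of which the documents support:

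- *That common follow-up scans fit no category.* The documents give no frequencies, and a count of states does not measure how often they occur.
- *That the rules fail the very case iRECIST was chosen for, an unchanged new lesion.* The rationale says "The appearance of new lesions may not represent progressive disease with immunotherapy", but says nothing about a new lesion unchanged at the repeat scan. That case also depends on how no new lesion is read.
- *That like patients would be treated differently.* In the Section 8.1.1 imaging and treatment table, clinically stable patients with iUPD, iSD, iPR or iCR may all continue at the investigator's discretion, and clinically unstable patients discontinue in all of these. Imaging differs little, since the repeat scan for iUPD may fall at the next scheduled visit.

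Finally, the SAP takes best iRECIST response across all time points under RECIST 1.1 and iRECIST, so a response before iUPD, or a later scan that qualifies, still counts.

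**Conclusion.** The point holds in limited form. The non-target condition for iPR and iSD gives a wrong result when non-target lesions have cleared, whether the scan is left unlabelled or defaults to iUPD: 2 of 24 non-iCPD states. It can turn a responder into an iPFS event and remove a response seen only after iUPD from iORR and iDoR. The rule for remaining iUPD is incomplete rather than wrong: unchanged non-target progression, and an unchanged new lesion if no new lesion means none present, rest on a default that is implied but not stated.

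This assumes that the protocol's own text governs label assignment. Frequency is unknown. Only the exploratory iRECIST endpoints are affected; the RECIST 1.1 endpoints are not, and no material consequence for treatment handling is shown. The correction is still worth making because the fault is specific and costs little to remove.

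**What to change.** In Protocol Section 8.1.1:

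1. Replace the non-target condition for iPR and iSD with: *non-target lesions are not iUPD (iCR, non-iCR/non-iUPD, or none at baseline)*.
2. Replace the rule for remaining iUPD with: *no iCPD criterion is met, and any lesion category that caused iUPD (target, non-target or new) still meets the PD threshold or persists*. A new lesion that persists then keeps the scan at iUPD, which settles what no new lesion means. The rule also catches target growth of less than 5 mm above the threshold, which is at present neither iCPD nor unworsened.
3. Correct not unconfirmed to not confirmed in the lead-in.

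In SAP Section 5.4.8.3, state that iORR, iPFS and iDoR are derived from these definitions.

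Check on the 24 states: 6 (target) + 9 (new lesion) + 3 (non-target) = 18 iUPD; the other 6 become 1 iCR, 3 iPR and 2 iSD. None is left unlabelled.

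Cost: protocol wording and matching derivation text. No new scans, visits or data.

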8.1.2. Criteria Required to Receive Treatment during Confirmatory Scan Period

In order for patients to continue receiving study drugs, the following criteria apply:

- absence of clinically significant deterioration
- absence of clinical symptoms indicating clinically significant disease progression
- no decline in performance status
- no significant, unacceptable, or irreversible toxicities related to study treatment
- patient must sign the addendum consent prior to being treated during this time period

